5.2 Ocular Adverse Events

The number of subjects reporting at least one AE of a given type specified in the protocol will be summarized. Ocular AEs not specified in the protocol (i.e., recorded as “other” and written in rather than selected from the list) that occur during the study will coded by MedDRA preferred term and summarized. Each AE will be summarized by incidence (numerator), denominator, percentage and 95% confidence interval. The summarization will be conducted using the FREQ procedure and the count, percent and exact Clopper-Pearson 95% binomial confidence intervals will be reported. Protocol-specified and other AEs will also be provided in separate listings.

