4.2 Protocol Background and Rationale

Protocol TMI-09-01, also known as the COMPASS Trial, was a prospective, randomized, comparative multicenter study to assess the safety and effectiveness of the CyPass Micro-Stent in subjects with primary open angle glaucoma who were undergoing cataract surgery. In the study, a total of 505 subjects were randomized to one of two treatment groups, as follows: The CyPass group underwent cataract surgery and received the CyPass Micro-Stent, while the Control group underwent cataract surgery alone. All subjects randomized were followed for 2 years postoperatively.

The study was performed in 2 phases. During the initial phase, 75 subjects were randomized. After FDA review of 3 month or longer postoperative data on these subjects, approval was granted for enrollment and randomization of the remaining 430 subjects in the study expanded phase. Enrollment in the initial study phase began in September 2009 and ended in August 2010. Enrollment in the expanded phase of the study began in July 2011 and the last study subject was randomized in March 2013.

**CYPASS® MICRO-STENT
PROTOCOL TMI-09-01-E VERSION G**

Subjects enrolled in the COMPASS Trial were examined at 2 preoperative visits to confirm eligibility for study participation. The first visit (Screening Visit) involved a comprehensive ophthalmic examination. Subjects qualifying after completion of the Screening Visit were required to discontinue use of ocular hypotensive medication, or “washout”, for a pre-established period to remove the medication from their system. After washout, subjects returned for a Baseline Visit during which they were re-evaluated and additional baseline data was collected to confirm continued eligibility. Subjects who qualified after the Baseline Visit were scheduled for cataract surgery. After completion of uncomplicated cataract surgery, subjects were randomized intraoperatively to either the CyPass group or the Control group. Subjects were asked to return for examination at postoperative Day 1, Week 1, Month 1, Month 3, Month 6, Month 12, Month 18 and Month 24.

Study protocol TMI-09-01-E, the COMPASS Extension Trial, is designed to collect safety data beyond 24 months postoperatively for subjects who completed study protocol TMI-09-01. [REDACTED]
[REDACTED] Study enrollment was initiated April 2016.

**CYPASS® MICRO-STENT
PROTOCOL TMI-09-01-E VERSION G**

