8.2 Study Visits

All subjects enrolled will return for defined follow-up visits through 60 months post-randomization in the COMPASS Trial. The number of scheduled study visits required will be dependent on the date of subject randomization in the COMPASS Trial. Data collected from each study visit will be recorded on an electronic Case Report Form (eCRF).

8.2.1 36 Month Postoperative Visit

This visit will occur at postoperative day 1095 ± 90 days. The following information will be captured for the study eye at this visit:

- Manifest refraction and ETDRS BCVA
- Slit lamp biomicroscopy
- Goldmann tonometry
- Dilated fundus examination and C:D ratio assessment
- Visual field mean deviation
- Gonioscopy examination (CyPass-implanted eyes only)
- Central corneal pachymetry
- Specular microscopy
- Ocular hypotensive medications
- AE assessment
- Subject Symptom Questionnaire

In the event a subject is enrolled who is more than 36 months postoperative, retrospective data for the 36-month follow-up period, if available, may be collected from review of the subject's medical chart.

**CYPASS® MICRO-STENT
PROTOCOL TMI-09-01-E VERSION G**

8.2.2 48 Month Postoperative Visit

This visit will occur at postoperative day 1460 ± 90 days. The following information will be captured for the study eye at this visit:

- Manifest refraction and ETDRS BCVA
- Slit lamp biomicroscopy
- Goldmann tonometry
- Dilated fundus examination and C:D ratio assessment
- Visual field mean deviation
- Gonioscopy examination (CyPass- implanted eyes only)
- Central corneal pachymetry
- Specular microscopy
- Ocular hypotensive medications
- AE assessment
- Subject Symptom Questionnaire

In the event a subject is enrolled who is more than 48 months postoperative, retrospective data for the 48-month follow-up period, if available, may be collected from review of the subject's medical chart.

8.2.3 60 Month Postoperative Visit

This visit must occur at postoperative day 1825 ± 90 days. The following information will be captured for the study eye at this visit:

- Manifest refraction and ETDRS BCVA
- Slit lamp biomicroscopy
- Goldmann tonometry
- Dilated fundus examination and C:D ratio assessment
- Visual field mean deviation
- Gonioscopy examination (CyPass-implanted eyes only)
- Central corneal pachymetry
- Specular microscopy
- Ocular hypotensive medications
- AE assessment
- Subject Symptom Questionnaire

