1. STUDY DESIGN & OUTCOMES

Study Protocol TMI-09-01-E (the COMPASS Trial Extension) is a multicenter observational study. Up to 480 subjects randomized in the Study Protocol TMI-09-01 (the COMPASS Trial) at up to 24 investigational sites may participate. Study data through 5 years post-randomization in the COMPASS Trial will be collected for subjects who consent to participate.

This statistical analysis plan (SAP) presents the details of the statistical methodologies for the analysis of data for Study Protocol TMI-09-01-E (Version G, dated 26 October 2016). The purpose of this research study is to evaluate the long-term safety of the CyPass Micro-Stent in subjects who completed the COMPASS Trial.

Primary Outcome

- Rate of occurrence of sight-threatening adverse events (AE)

Secondary Outcomes – Safety

- Best Corrected Visual Acuity (BCVA)
- Rate of occurrence of ocular adverse events (AE)
- Slit lamp, gonioscopy and fundus findings
- Visual field loss mean deviation (MD)
- Central corneal thickness (CCT)
- Central corneal endothelial cell density (ECD)
- Rate of occurrence of CyPass movement, defined as a change by at least 1 in the number of CyPass rings visible (e.g., from 0 rings to 1 ring or from 3 rings to 2 rings) that does not result in clinical sequelae (e.g., secondary surgical intervention to modify device position, corneal endothelial touch by device, corneal edema leading to loss of BCVA > 2 lines at the last postoperative visit in comparison with preoperative BCVA, progressive corneal endothelial cell loss (ECL), erosion of device through sclera, or device obstruction requiring secondary surgical intervention), and that is not attributable to:
 - variations in gonioscopic viewing angle or illumination,
 - changes in angle anatomy due to concomitant findings such as resolution of hyphema,
 - changes in anterior chamber depth, or
 - development of focal peripheral anterior synechiae.

Secondary Outcomes – Effectiveness

- Mean change in intraocular pressure (IOP)
- Proportion of subjects who are not using ocular hypotensive medication with $\geq 20\%$ reduction in IOP from baseline in the COMPASS Trial
- Proportion of subjects who are not using ocular hypotensive medication with IOP ≥ 6 mmHg and ≤ 18 mmHg

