4. GENERAL STATISTICAL CONSIDERATIONS

Unless noted otherwise, continuous variables will be characterized with the number of non-missing values, means, standard deviations, medians, minimums, and maximums while categorical variables will be characterized by frequencies (numerators), denominators, and percentages. There are no hypotheses tested in this study. All confidence intervals will be 95% confidence intervals and will be two sided. Confidence intervals for continuous variables will be based on the t distribution. Confidence intervals for categorical variables be calculated using the exact Clopper-Pearson 95% binomial formula. If there is a special case for a one sided interval, then that interval will be a 97.5% one-sided confidence interval.

All statistical analyses will be conducted using SAS[®] software, Version 9.4 of the SAS System for Windows or higher.

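### SAP 5.2 reports ocular AEs only as crude percentages, with no common at-risk period, although prospective follow-up runs from none to about two years by randomisation date

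*SAP*

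**What the plan says.** **Analysis.** Protocol 3.4.2 and 5.1.2 and SAP 1 name the secondary safety outcome as a rate of occurrence of ocular AEs. SAP 5.2 delivers a proportion: "Each AE will be summarized by incidence (numerator), denominator, percentage and 95% confidence interval". On method it says that "the count, percent and exact Clopper-Pearson 95% binomial confidence intervals will be reported". Protocol 9.2 adds nothing on exposure. Neither section defines the denominator or the period at risk, and neither says that the table is by treatment group. SAP 3 makes everyone enrolled in the extension, up to 480 subjects, the analysis population. SAP 4 states: "There are no hypotheses tested in this study".

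**Follow-up.** Protocol 8.2 acknowledges that follow-up is unequal: "The number of scheduled study visits required will be dependent on the date of subject randomization in the COMPASS Trial". Protocol 4.2 gives the dates:
- Initial phase: "During the initial phase, 75 subjects were randomized", and "Enrollment in the initial study phase began in September 2009 and ended in August 2010".
- Expanded phase: 430 subjects, randomised July 2011 to March 2013.
- Extension: enrolment opened in April 2016.

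The last scheduled visit is at day 1825 ± 90. Protocol 3.3 and 8.2 permit, but do not require, chart data for the 36-, 48- and 60-month periods, and they foresee subjects enrolling after Month 60.

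**What counts as an event.** Under Protocol 10, AEs still ongoing from COMPASS that meet the definitions are recorded as AEs of this study. Several definitions in Protocol 10.1 compare the current state with a COMPASS reference: best BCVA, Month 24 cup-to-disc ratio, Month 24 visual field MD and baseline ECD.

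**Contrast.** SAP 5.1 gives the primary outcome, sight-threatening AEs, a Kaplan-Meier analysis with censoring and annualised rates. Other ocular AEs get nothing comparable. SAP 6 uses observed data only.

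**The concern.** A binomial percentage reads as a risk over a period shared by all subjects. Here there is no such period. Two subjects in the same table may have been watched for two years and for no prospective time at all, with the gap filled or not filled by whatever the chart holds. The same underlying hazard can then give quite different percentages, depending on who enrolled, when, and how complete the charts were. The Clopper-Pearson interval reflects none of this.

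As no hypothesis is tested, the absolute figures are the result. A reader of a long-term safety report is likely to take the ocular AE percentages as five-year or post-Month-24 risks, and the table as planned does not support that reading.

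**Working it through.** The documents state no ocular AE rate, so there is no figure to reproduce. The building blocks agree with each other: 75 + 430 = 505 randomised, and 36, 48 and 60 months are 1095, 1460 and 1825 days.

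**Step 1: prospective time inside the window.** Randomisation was intraoperative (Protocol 4.2), so postoperative day and day since randomisation coincide. Prospective time = randomisation date + 1825 days (or + 1915 with the +90-day window) − 1 April 2016, floored at zero.

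| Subject | Month reached on 1 April 2016 | Time left to day 1825 | Time left to day 1915 |
|---|---|---|---|
| First initial-phase (1 Sept 2009) | 79 | none | none (passed 16.1 months before) |
| Last initial-phase (31 Aug 2010) | 67 | none | none (passed 4.1 months before) |
| First expanded-phase (1 July 2011) | 57 | 2.9 months | 5.9 months |
| Last expanded-phase (31 March 2013) | 36 | 23.9 months | 26.9 months |

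Later entry shortens every figure. The time after Month 24 that only charts can cover is about 12 months for the last subject and the whole 36 months for the initial phase.

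**Step 2: what a crude percentage would show.** Assumptions, none from the documents: constant hazard λ from Month 24 to 60; transient events seen only prospectively or through charts; uniform accrual in the expanded phase; no dropout; extension participation in the parent-trial mix (75/505 = 14.9% initial phase). With t prospective years and c the share of earlier time captured from charts,

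expected crude percentage = average of 1 − exp(−λ[t + c(3 − t)]).

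For a true Month 24-60 risk of 10%, λ = −ln(0.90)/3 = 0.0351 per year. In the expanded phase t is uniform from 0.244 to 1.993 years, mean 1.117.

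With c = 0, the expanded phase gives 3.83% and the initial phase 0%, so the mixture is 0.851 × 3.83% = 3.3%. With c = 0.5, the initial phase gives 1 − exp(−0.0351 × 1.5) = 5.1% and the expanded phase 6.97%, so the mixture is 0.851 × 6.97% + 0.149 × 5.1% = 6.7%.

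| True Month 24-60 risk | No capture | 50% | 90% | Complete |
|---|---|---|---|---|
| 5% | 1.6% | 3.3% | 4.7% | 5.0% |
| 10% | 3.3% | 6.7% | 9.4% | 10.0% |
| 20% | 6.7% | 13.6% | 18.8% | 20.0% |

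**Step 3: enrolment mix and entry date** (true risk 10%, no capture).

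| Entry | 0% initial phase | 14.9% | 30% |
|---|---|---|---|
| April 2016 | 3.8% | 3.3% | 2.7% |
| Six months later | 2.2% | 1.9% | 1.5% |

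**Step 4: interval and exposure-adjusted rate.** Take 480 subjects, April 2016 entry and no capture. Eye-time = 480 × 0.851 × 1.117 ≈ 457 eye-years. At a true risk of 10%, about 16 subjects have an event. The crude result is 16/480 = 3.3% (95% CI 1.9 to 5.4), an interval that excludes 10%. The rate is 16/457 = 3.5 per 100 eye-years, and 1 − exp(−3 × 0.035) = 10.0%, which recovers the assumed risk.

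**Step 5: where dividing by eye-time would mislead.** Suppose instead a persistent AE accrues from Month 24 and is always found by Month 60. The crude percentage is then 10%, which is correct. Dividing it by mean expanded-phase time since consent gives 0.10/1.117 = 9.0 per 100 eye-years, about 2.5 times the true 3.5. Numerator and eye-time must cover the same period.

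**The case against.** The strongest reply is that the direction of any distortion is not established. A reader might infer that the planned percentages understate ocular AE risk across the board. The documents do not support that. Chart data are allowed for each visit period, and the shortfall vanishes as capture becomes complete. Persistent states judged against a COMPASS reference can be found at a single late visit. AEs carried over from COMPASS push percentages up. The understatement is expected only for transient events that were not charted. This part of the reply stands.

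A second reply is that exposure adjustment can do harm. It also stands: step 5 shows the inflation if persistent or carried-over events are divided by time since consent, and an initial-phase subject could bring events with no in-window eye-time. It limits the remedy to new-onset events over matching eye-time.

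Third, SAP 5.2 does not define its denominator, so the presence of initial-phase subjects in it is a reading, though the natural one given SAP 3. Nor does the SAP say that the table estimates Month 24-60 risk. Both are fair, and both are reasons to define the quantity.

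Fourth, it would go too far to call the Clopper-Pearson interval invalid: it is usable for the proportion of subjects with a recorded AE. That proportion is simply not a risk over a stated period.

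Finally, the table is secondary and descriptive, and the primary outcome is handled with censoring. If uptake is similar in the two arms, randomisation should also give them similar follow-up, so the difficulty lies mainly in absolute rates. This lowers the priority of the point but does not remove it.

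**Conclusion.** The concern holds in limited form. The ocular AE outcome is called a rate but is analysed as a crude percentage with no at-risk period, while prospective in-window follow-up ranges from none to about two years by design. That range follows from the documents' own dates. It follows that the percentages depend on phase mix, entry date and chart completeness.

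The size depends on assumptions. At an assumed true Month 24-60 risk of 10%, the planned table could show anything from about 3.3% to 10% according to chart capture alone, and about 1.5% to 3.8% across the phase mixes and entry dates tried with no capture. These figures apply to transient events under constant hazard, uniform accrual and no dropout. They do not show that the actual results will be too low. For persistent-state and carried-over AEs the net direction cannot be settled from the documents.

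This is a cheap improvement to a secondary table. It does not touch the primary analysis.

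**What to change.** In SAP 5.2, keep the crude table, state its denominator, and present it by treatment group. Add for each group:
- total eye-years, and the rate of subjects with a first new-onset AE per 100 eye-years, with an exact Poisson 95% CI;
- a counting rule that admits only events with onset after extension consent, over eye-time from consent to first event or last contact.

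Tabulate separately, as proportions and outside that rate:
- AEs ongoing from COMPASS;
- chart-derived events dated before consent;
- state-type AEs already present at the first extension visit.

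An eye that already has a given AE at entry is not at risk of a first occurrence and should add no eye-time for that AE.

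The cost is modest: eye-time must be derived per AE type and events classified by source and onset, but no new examinations are needed. The rate assumes a roughly constant hazard, and initial-phase subjects will add little or no in-window eye-time, so it will describe mainly the expanded phase. The SAP should say so.

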5.3 Central Corneal Thickness (CCT)

CCT data collected at baseline, 12 month and 24 month postoperative visits in Protocol TMI-09-01 (the COMPASS trial) and collected in this protocol will be summarized with N, mean, standard deviation, minima, median, and maxima. A 95% confidence interval will be provided for the actual change and percentage change from baseline. Change between 2 consecutive visits will also be summarized.

For the tabulation of actual change and percent change, there will be two sets of tables. The first will use the preoperative CCT from the COMPASS Trial as a baseline value. The second will use the 24-month visit CCT from the COMPASS Trial as the baseline value.

All calculations will be performed using the MEANS procedure and the results will be reported for each of the visits and treatment groups. Descriptive statistics for the changes between consecutive visits will also be calculated using the MEANS procedure.

5.4 Central Corneal Endothelial Cell Density

Endothelial cell density (ECD) data collected at baseline, 3 month, 6 month, 12 month and 24 month postoperative visits in Protocol TMI-09-01 (the COMPASS trial) and at each XT scheduled follow-up visit will be summarized with N, mean, standard deviation, minima, median, and maxima for each treatment arm. A 95% confidence interval will be provided for the change and percentage change in ECD from baseline. The change between 2 consecutive visits will also be summarized.

All descriptive statistic calculations will be made from the MEANS procedure and the results reported for each of the visits and treatment groups. Descriptive statistics for the changes between consecutive visits will also be calculated using the MEANS procedure.

5.5 Best Corrected Visual Acuity

Best Corrected Visual Acuity (BCVA) data collected at the subject's baseline, 12 month and 24 month postoperative visits in Protocol TMI-09-01 and at each XT scheduled follow-up visit will be summarized as counts (numerators), denominators, and percentages with 95% confidence intervals for subjects who have BCVA 20/20 or better, 20/25 or better, 20/32 or better, 20/40 or better and worse than 20/40. Because BCVA was collected in the COMPASS trial as TLR, TLR values will be converted to Snellen and logMAR Visual Acuity using a conversion table to be approved by Alcon and included in an appendix to the TLFs. Also, shift tables from baseline will be presented with counts (numerators), denominators, percentages, and 95% confidence intervals for Snellen Visual Acuity.

The summarization will be performed via the FREQ procedure and the count, percent, and exact Clopper-Pearson 95% binomial confidence intervals will be reported.

5.6 Slit Lamp, Gonioscopy and Fundus Exam Findings

Slit lamp, gonioscopy, and fundus examination findings at month 36, 48, and 60 will be tabulated such that the number (numerator), denominator, and percentage of subjects in each category and 95% confidence intervals for the percentages will be summarized by each XT scheduled follow-up visit. The summarization will be performed via the FREQ procedure and the count, percent, and exact Clopper-Pearson 95% binomial confidence intervals will be reported.

In addition, a listing of study subjects with one or more Cypass rings visible at each visit will also be provided.

5.7 Visual Field Loss Mean Deviation

The visual field mean deviation (MD) testing data collected at baseline, 3 month, 6 month, 12 month and 24 month postoperative visits in Protocol TMI-09-01 and in this protocol will be summarized with N, mean, standard deviation, minima, median, and maxima. A 95% confidence interval will be provided for the change and percentage change from baseline.

All calculations will be made from PROC MEANS and the results reported for each of the visits and treatment groups. For the tabulation of change and percent change, there will be two sets of tables, the first will use the baseline from the COMPASS Trial, and the second will use the 24 month visit value from the COMPASS Trial.

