10.1 Ocular Adverse Events

Ocular AEs that might reasonably be expected to occur include, but are not limited to, the following:

- BCVA loss of 2 lines (10 letters) or more on the ETDRS chart in comparison with the best BCVA reported in Study Protocol TMI-09-01
- Any 2-point worsening in slit lamp examination findings (other than cells and flare) to “severe or “very severe”, which is not associated with a pre-existing condition
- Chronic anterior uveitis, defined as inflammation of Grade 1+ or worse persisting for more than 3 months post-operatively or that recurs less than 3 months after discontinuation of anti-inflammatory treatment
- Endophthalmitis
- Presence of flat anterior chamber requiring anterior chamber reformation
- Presence of a shallow chamber with iridocorneal apposition without lens/cornea touch
- Corneal edema
- Corneal decompensation
- Corneal opacification
- Hyphema, which is > 2 mm in size
- Retinal detachment
- Proliferative vitreoretinopathy
- Other retinal complications (e.g., dialysis, flap tears)
- Increase in C:D ratio of ≥ 0.3 units in comparison with the 24-month C:D ratio reported in Study Protocol TMI-09-01
- A confirmed worsening in visual field mean deviation (MD) of ≥ 2.5 dB compared to the 24-month visual field MD determined in Study Protocol TMI-09-01
- Suprachoroidal hemorrhage
- Choroidal effusion requiring surgical drainage

**CYPASS® MICRO-STENT
PROTOCOL TMI-09-01-E VERSION G**

- Choroidal effusion or detachment with at least a partially hemorrhagic component that obstructs vision or causes pain (including both peripheral and “kissing” choroidal detachments) lasting longer than 30 days
- Hypotonic maculopathy
- Macular edema (including cystoid macular edema and diabetic macular edema)
- Choroidal folds
- Other maculopathy
- Clinically significant hypotony, which is defined as IOP < 6 mmHg that results in maculopathy; flat anterior chamber requiring reformation; corneal folds; onset or worsening of with-the-rule astigmatism by ≥ 1 Diopter or rotation of against-the-rule to with-the-rule astigmatism by ≥ 1 Diopter; choroidal effusion requiring surgical drainage; suprachoroidal hemorrhage or BCVA loss of ≥ 2 lines
- Mean (or median) IOP ≥ 10 mmHg higher than the subject’s baseline mean unmedicated diurnal IOP reported in Protocol TMI-09-01
- CyPass device obstruction by iris, vitreous, lens, fibrous overgrowth, fibrin or blood
- CyPass device malfunction

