6. METHODS FOR HANDLING MISSING DATA

Since this is a safety observation study, no imputations of the data will be made. All tables and figures will be generated using observed data only.

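### Mean percentage change in visual field MD, with its t-based interval, is unreliable when reference values lie near or above 0 dB; drop it and keep the dB change

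*SAP*

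**What the plan says.** SAP 5.7 summarizes MD by visit and treatment group with PROC MEANS and adds: "A 95% confidence interval will be provided for the change and percentage change from baseline". Protocol 9.7 carries the same sentence. The SAP then doubles the output: "For the tabulation of change and percent change, there will be two sets of tables", of which "the first will use the baseline from the COMPASS Trial, and the second will use the 24 month visit value from the COMPASS Trial". SAP 4 fixes the method: "Confidence intervals for continuous variables will be based on the t distribution". It also states: "There are no hypotheses tested in this study". SAP 6 adds that "no imputations of the data will be made".

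Neither document gives a formula for percentage change, says whether the denominator is signed or absolute, or says what to do with a reference at, near or above 0 dB. The extension's eligibility criteria (Protocol 7.1 and 7.2) set no limit on MD.

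**The concern.** A percentage change makes sense for a quantity that is strictly positive with a true zero, as corneal thickness and endothelial cell density are. MD is different. It measures departure from a normal reference in dB, so 0 is the normal value and either sign can occur. That property comes from the measure itself; the documents do not spell it out.

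Dividing by such a score has three consequences:

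- The ratio does not exist at a reference of 0 dB. With observed data only, that eye drops out of the percentage column but stays in the dB column, so the two can have different N.
- Near 0 dB the ratio is very large, and a few eyes can set the mean and the width of the interval.
- With a signed denominator, worsening reads as a positive percentage from a negative reference and as a negative percentage from a positive one. Both kinds are averaged in one column.

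The study's output is its descriptive safety tables. Someone comparing arms on mean percentage change in MD could be misled by a handful of eyes.

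**Working it through.** **Inputs from the documents.** Statistic and two references: SAP 5.7 and Protocol 9.7. Two-sided 95% t-based interval: SAP 4. Size of worsening used for illustration: 2.5 dB, the threshold in Protocol 10.1. Maximum enrolment: 480 in total (SAP 1); the split between arms is not given. The plan states no MD value or precision figure, so there is none to reproduce.

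**Step 1: arithmetic, no assumptions.** Signed: 100 × (follow-up − reference) / reference. Absolute: the same divided by |reference|. For a change of −2.5 dB:

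| Reference (dB) | Signed | Absolute |
|---|---|---|
| −10 | +25% | −25% |
| −2.5 | +100% | −100% |
| −0.1 | +2500% | −2500% |
| 0 | undefined | undefined |
| +0.5 | −500% | −500% |

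**Step 2: simulation, assumed distributions.** 4000 trials per row, 250 eyes. Reference is normal with the mean/SD shown; change is normal with mean −1 dB and SD 1 dB. Values are rounded to 0.01 dB (0.1 dB in the third column), and eyes at exactly 0 dB are excluded from the percentage. Wrong sign means that the trial mean reads as improvement although the true mean change is a 1 dB worsening: below 0 for the signed form, above 0 for the absolute form.

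| Reference mean/SD (dB) | Signed: wrong sign | Signed, MD to 0.1 dB: wrong sign | Signed: interval includes 0 | Signed: median half-width (points) | Absolute: wrong sign |
|---|---|---|---|---|---|
| −2/2 | 21% | 2.1% | 79% | 77 | 0.0% |
| −3/3 | 24% | 5.0% | 81% | 56 | 0.1% |
| −4/4 | 24% | 7.3% | 82% | 45 | 0.15% |
| −3/2 | 13% | 0.2% | 58% | 48 | 0.1% |
| −6/3 | 8% | 0.4% | 32% | 14 | 0.3% |
| −8/2 | 0% | 0% | 0% | 2 | 0% |

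In the first five rows the three most extreme eyes carry a median 82-86% of the variance of signed percentage change; in the last row, 16%. At least one eye falls at exactly 0 dB in 26%, 18%, 15%, 15%, 4% and 0% of trials, in row order.

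**Step 3: does an absolute denominator rescue the mean?** It largely fixes the sign, but the trial mean still varies widely. Its central 95% range is −294% to −82% at −2/2, −204% to −47% at −3/2 and −109% to −18% at −6/3, against −16% to −12% at −8/2. At 0.1 dB the ranges narrow to −138% to −73% at −2/2 and −47% to −20% at −6/3. The answer therefore depends on recording precision, which is a defect in itself.

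**Step 4: sensitivity.**

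- With a change SD of 2 dB, signed wrong-sign rates rise to 31%, 31%, 33%, 21%, 12% and 0% in row order. The absolute form is wrong in 1.9-3.5% of trials in the first five rows.
- More eyes help little. With a change SD of 2 dB and references of −3/3, the signed mean is wrong in 33.0% of trials at n = 100 and 32.3% at n = 240.
- With references far from zero (−12/3, change SD 2 dB, n = 240), the trial mean ranges only from +6% to +11%.

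**Step 5: the dB change.** It has the right sign in every simulated trial. The half-width is about 1.97 × 1/√250 = 0.12 dB at change SD 1, and 1.97 × 2/√240 = 0.25 dB at change SD 2, whatever the reference distribution.

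**The case against.** The strongest reply is that exposure is not shown. The documents give no MD distribution and no recording precision. Three of the six scenarios set the SD equal to the size of the mean, which places about 16% of eyes above 0 dB by construction. At −8/2 the problem vanishes, and at 0.1 dB precision the wrong-sign rates fall sharply. This stands as a limit on size. The simulated percentages show what can happen and do not predict this trial. The arithmetic in step 1 does not depend on them, and nothing in the plan guards against references near zero.

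A second reply is that an alert reader would notice. The dB change appears alongside, and SAP 4 requires N, SD, median, minimum and maximum, so a 2500% maximum or a lost eye would be visible. That is true, and it keeps the severity low, but it does not make the mean or its interval useful.

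A third is that a narrower fix would do: define the denominator, add a 0 dB rule and report the median without an interval. The median percentage change is indeed robust, with the wrong sign in at most 0.02% of simulated trials. But an absolute denominator and a 0 dB rule leave the mean unstable, and the percentage serves no stated purpose. The protocol's own MD criterion is absolute: "A confirmed worsening in visual field mean deviation (MD) of ≥ 2.5 dB". Deletion is simpler and loses no data.

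Last, Protocol 12.2 requires written approval from the sponsor and the overseeing IRBs for any protocol change. That cost is real and is counted in the fix.

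**Conclusion.** The point holds. As written, the plan produces a mean percentage change in a signed dB score, with a t-based interval, that is undefined at 0 dB and unreliable when references lie near or above it. Leaving the denominator undefined makes this worse, but defining it would not repair the mean.

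The size depends on an MD distribution that the documents do not give. It is material for assumed reference means of about −2 to −6 dB with the SDs tried, and negligible when references lie well below zero. The defect is confined to the mean percentage change and its interval. The dB change is sound, the median percentage change is not seriously affected, and the percentage changes in corneal thickness and cell density are not touched.

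Severity is low: no hypothesis test or decision rule uses percentage MD, and the primary outcome is unaffected. The change is worth making because it is cheap.

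**What to change.** Delete percentage change for MD and keep the dB change with its 95% interval for both references:

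1. Protocol 9.7: limit the interval to the change in dB from baseline.
2. SAP 5.7, first paragraph: make the same edit.
3. SAP 5.7, second paragraph: limit the two sets of tables to the change in dB, leaving the two references as they are.

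The cost is three sentence edits and the removal of the percentage rows from both sets of MD tables. No new data are needed. The Protocol 9.7 edit needs the sponsor and IRB approval set out in Protocol 12.2. If that is out of proportion for one descriptive column, edit the SAP alone and record the change there as a departure from Protocol 9.7.

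Optionally, add n/N and percentage of eyes by arm and visit with MD worsening of 2.5 dB or more from month 24, labelled as confirmed or unconfirmed. SAP 5.2 already covers the confirmed event ("The number of subjects reporting at least one AE of a given type specified in the protocol will be summarized"), so such a table would have to be reconciled with that summary.
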